11.3. Procedures for Handling Special Situations

11.3.1. Pregnancy and Breastfeeding

Note: Pregnancy per se is not considered to be an AE; however, it is discussed here because of the importance of reporting pregnancies that occur during studies and because a medical occurrence observed in the mother or fetus/newborn would be classified as an AE.

Female patients of childbearing potential and fertile male patients will be informed as to the potential risk of conception while participating in this study and will be advised that they must use highly effective contraception listed below (i.e., results in a low failure rate when used consistently and correctly) during the dosing period and for a period of at least 4 months after the EoT.

Highly effective methods include:

- Combined (estrogen and progestogen containing) hormonal contraception associated with inhibition of ovulation:
 - Oral
 - Intravaginal
 - Transdermal
- Progestogen-only hormonal contraception associated with inhibition of ovulation:
 - Oral
 - Injectable
 - Implantable
- Intrauterine device
- Intrauterine hormone-releasing system
- Bilateral tubal occlusion
- Vasectomized partner
- Sexual abstinence

A pregnancy test will be performed on each premenopausal female patient of childbearing potential prior to the first dose of study drug, at screening, and again at treatment discontinuation during the

EoT. A negative serum hCG pregnancy test must be documented within 3 days prior to first study dose on C1D1.

If a patient is confirmed pregnant during the study, study drug administration must be discontinued immediately. The Investigator must immediately notify the Sponsor's Medical Monitor of the event and record the pregnancy on the Pregnancy Form (provided by Karyopharm). The initial information regarding a pregnancy must be forwarded to Karyopharm's Pharmacovigilance by email or fax within 24 hours of first knowledge of its occurrence.

The pregnancy should be followed up to determine the outcome, including any spontaneous or voluntary termination, details of the birth, and any birth defects, congenital abnormalities, or maternal and/or newborn complications.

All pregnancies occurring within 4 months after the patient's last dose of study drug must be reported to Karyopharm, regardless of whether the patient received selinexor or other study drugs, withdraws from the study, or the study is completed. Patients should be instructed to inform the Investigator regarding any pregnancies.

Any SAE that occurs during pregnancy must be recorded on the SAE report form (e.g., maternal serious complications, therapeutic abortion, ectopic pregnancy, stillbirth, neonatal death, congenital anomaly, or birth defect) and reported within 24 hours in accordance with the procedure for reporting SAEs (described in Section 11.2.3)

A pregnancy in a female partner of a male patient must be reported to Karyopharm within 24 hours of learning of its occurrence. Pregnancies in female partners should only be followed if the male patient is being treated with a selinexor-containing regimen. Consent to report information regarding these pregnancy outcomes should be obtained from the female partner.

It is not known whether selinexor passes into the breast milk. Mothers should not breastfeed while being treated with selinexor-containing regimen.

11.3.2. Abuse, Misuse, Medication Errors, Overdose, and Occupational Exposure

All incidences of abuse, misuse, medication errors, overdose, and occupational exposure are required to be reported to Karyopharm Pharmacovigilance regardless of whether or not there is an associated AE or SAE. Reporting should be completed via the electronic SAE Report Form when technically possible. To complete the electronic SAE Report Form, a Log Line must first be completed in the Medication Error eCRF. The incident will then be linked to an electronic SAE Report Form. If electronic reporting is not possible, reporting should be completed via a paper SAE Report Form emailed to [contact].

11.3.2.1. Abuse, Misuse, or Medication Error

Abuse is the persistent or sporadic, intentional excessive use of the study treatment which is accompanied by harmful physical or psychological effects.

A medication error is any preventable incident that may cause or lead to inappropriate study treatment use or patient harm while the study treatment is in the control of the health care professionals or patients. Such incident may be due to health care professional practice, product labeling, packaging and preparation, procedures for administration, and systems, including the

following: prescribing, order communication, nomenclature, compounding, dispensing, distribution, administration, education, monitoring, and use.

All occurrences of abuse, misuse, or medication error with any study treatment are to be recorded on an SAE report form and sent to Karyopharm Pharmacovigilance, regardless of whether or not an AE or SAE has occurred due to the abuse, misuse, or medication error. If the abuse, misuse, or medication error is associated with an SAE, the SAE report form must be submitted to Karyopharm Pharmacovigilance within 24 hours of awareness. If there is no AE or SAE, the report must be submitted within 24 hours of awareness.

11.3.2.2. Overdose

An overdose is a deliberate or accidental administration of any study treatment to a study patient, at a dose greater than that which was assigned to that patient per the study protocol. If an overdose occurs, the Investigator and Karyopharm should be notified immediately, and the patient should be observed closely for AEs. Resulting symptoms should be treated, as appropriate, and the incident of overdose and related AEs and/or treatment should be documented in the patient's medical record and in the eCRF. Information regarding the overdose is to be recorded on an SAE report form and sent to Karyopharm Pharmacovigilance, regardless of whether or not an AE or SAE has occurred due to the overdose. If the overdose is associated with an SAE, the SAE report form must be submitted to Karyopharm Pharmacovigilance within 24 hours of awareness. If there is no AE or SAE, the report must be submitted as soon as possible.

11.3.2.3. Occupational Exposure

Occupational exposure is the exposure to a study treatment as a result of one's professional or nonprofessional occupation. For this protocol, please follow the instructions for preparation and administration of selinexor.

All occurrences of occupational exposure with any study treatment are to be recorded on an SAE report form and sent to Karyopharm Pharmacovigilance, regardless of whether or not an AE or SAE has occurred due to the occupational exposure. If the occupational exposure is associated with an SAE, the SAE report form must be submitted to Karyopharm Pharmacovigilance within 24 hours of awareness. If there is no AE or SAE, the report must be submitted within 24 hours of awareness.

12. STATISTICAL CONSIDERATIONS

A statistical analysis plan (SAP) will be finalized prior to database lock. Any changes from the statistical analyses described in this document will be described in the SAP, and any deviation from the final SAP will be described in the clinical study report.

12.1. General Considerations

Summary tabulations will be provided for disposition, demographic, baseline characteristics, efficacy, and safety data as noted in the following sections. All data collected on the eCRF will be provided in by-patient data listings.

For categorical variables, summary tabulations of the number and percentage of patients within each category (with a category for missing data) of the parameter will be presented.

For continuous variables, the number of patients, mean, median, standard deviation, minimum, and maximum values will be presented. Time-to-event data will be summarized with Kaplan-Meier method using 50th (median) percentiles with associated 2-sided 95% CIs as well as percentage of censored observations if applicable.

12.1.1. Procedures for Handling Missing Data

In general, there will be no substitutions made to accommodate missing data points.

For time to event analyses, patients who have no efficacy evaluations will be considered as censored at date of first treatment.

For AEs, missing dates will be imputed per the rules outlined in the SAP. Each AE will be graded for severity according to NCI CTCAE. Missing severities of AEs will not be imputed and will be considered missing in any tabulations of AE severity. If an AE is missing a response to the question regarding relationship to treatment, the event will be considered to be related.

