12.4.1.2. Secondary Endpoints

- Progression-free survival is defined as time from date of first treatment to the date of first confirmed PD, or death due to any cause, whichever occurs first. Median PFS with 95% CI will be summarized for each treatment arm.
- Overall survival is defined as time to death, from the date of first treatment. Median OS with 95% CI will be summarized for each treatment arm.
- Complete response rate is defined as proportion of patients who achieved a CR. The point estimate and an 95% exact CI of CRR will be provided for each treatment arm.
- Duration of response is defined as the duration of time from first occurrence of response \geq PR until the first date of PD or death due to any cause, whichever occurs first. Median DOR with 95% CI will be summarized for each treatment arm.
- Disease control rate is defined as the percentage of patients who have achieved CR, PR or stable disease. The point estimate and an 95% exact CI of DCR will be provided for each treatment arm.

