1.6. Modifications to the Statistical Section of the Protocol

Not applicable. The current SAP is based on Protocol v3.0.

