4.3. Secondary Efficacy Endpoints

4.3.1. Definition of Secondary Efficacy Endpoints

Table 4-1 are the secondary efficacy endpoints:

Table 4-1 Efficacy Endpoints and Definitions

Endpoint	Definition
Secondary Endpoints	
Progression-free survival (PFS)	Duration of time from date of first study treatment until the first date that PD assessed by RECIST 1.1 is objectively documented or death due to any cause. Refer to Table 4-2 for details on PFS outcome status (PFS event vs. censored) and censoring definitions.
Overall survival (OS)	Duration from the date of first study treatment until death due to any cause. If death event did not occur during the follow-up period, the patient is censored at the date of discontinuation from the study (i.e. withdrawal of consent), or date of last participating visit (e.g., a telephone contact with patient status being alive) on or before database cutoff date, whichever occurs first.
Complete response rate (CRR)	Proportion of patients who achieved a CR per RECIST 1.1
Duration of response (DOR)	Duration of time from first meeting CR or PR measurement criteria (whichever occurs first) until the first date that PD recurrence is objectively

	documented or death due to any cause. Responses are assessed per RECIST 1.1.
	Refer to Table 4-2 or details on the outcome and censoring definitions.
Disease control rate (DCR)	Proportion of patients who have a response of CR, PR, or SD ≥ 12 weeks. Responses are assessed per RECIST 1.1.

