4.3.2.2. Analyses of Time to Event Secondary Endpoints

[figure not shown]
For each time to event secondary endpoint (PFS, OS and DOR), the number of patients with events, number of patients censored, estimates and 95% CI for the median of event time will be presented by treatment group.

[figure not shown]
Time-to-event will be plotted for each treatment group using the Kaplan-Meier method. The plot will include the number of patients at risk for each treatment group over time.

Table 4-2 PFS and DOR Outcome and Censoring Definitions

#	Situation	Date of event or censoring	Outcome
1	No baseline disease assessment	Date of first treatment	Censored
2	No adequate post-baseline disease status assessment unless death occurs prior to first post-baseline assessment	Date of first treatment	Censored
3	Documented PD without missing 2 or more consecutive assessments	Date of PD	Event
4	Death before documented PD and without missing 2 or more consecutive assessments	Date of death	Event
5	 No documented PD or death on or before Database cut Withdrawal of informed consent Lost to follow-up Date of discontinuation from treatment + 30 days Two or more consecutive missing assessments and the disease assessment result after the gap is PD¹ Start of new antineoplastic therapy, whichever occurs first 	Date of last adequate disease assessment prior to the events listed in the left column	Censored

^{1.} If disease assessment results after 2 or more consecutive missing assessments were not PD, the disease assessment gap will be ignored.

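### Protocol 12.1.1 censors patients without an efficacy evaluation at Day 1 and makes no exception for death, in undeclared conflict with the SAP, which counts such deaths in OS and PFS

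*Protocol*

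**What the plan says.** Protocol 12.1.1 (Procedures for Handling Missing Data) gives one rule for time-to-event analyses: "patients who have no efficacy evaluations will be considered as censored at date of first treatment". It names no endpoint and carves out no event.

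Protocol 12.4.1.2 defines the endpoints to which such a rule would apply. For OS: "Overall survival is defined as time to death, from the date of first treatment". For PFS: "time from date of first treatment to the date of first confirmed PD, or death due to any cause, whichever occurs first".

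The SAP handles the same patients differently. Table 4-1 defines OS as "Duration from the date of first study treatment until death due to any cause", and censors only patients who have not died, at study discontinuation or last participating visit. Table 4-2 (PFS and DOR) does use Day 1 censoring in row 2, but words the condition as "No adequate post-baseline disease status assessment unless death occurs prior to first post-baseline assessment". Row 4 makes a death before documented PD an event at the date of death, provided two or more consecutive assessments were not missed.

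On the link between the documents, protocol section 12 states: "Any changes from the statistical analyses described in this document will be described in the SAP". SAP 1.6, which is where such changes would be listed, reads: "Not applicable. The current SAP is based on Protocol v3.0".

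**The concern.** Patients who die before their first scan have the worst outcomes in the study. Censoring them at time zero takes them out of the Kaplan-Meier risk set before any event is counted, so a known death leaves no trace in the curve. Such censoring is informative and always flatters the result. With about 20 patients per arm and no concurrent control, one or two patients are enough to show in a median.

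The sentence also leaves two written rules for the same patients, with no statement of which was intended. For OS the disagreement reaches living patients as well: the protocol would censor an unscanned survivor at Day 1, while the SAP uses the last participating visit. For PFS the documents agree on living patients with no post-baseline assessment, so the conflict there is confined to deaths.

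**Working it through.** The documents give no figure for this rule, so there is nothing to reproduce. The check has two parts.

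**1. The rules side by side, for a treated patient who has a baseline scan and dies before the first post-baseline scan**

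| Source | OS | PFS |
|---|---|---|
| Protocol 12.1.1, literal | censored at Day 1 | censored at Day 1 |
| Protocol 12.4.1.2 | event at death | event at death |
| SAP Table 4-1 | event at death | refers to Table 4-2 |
| SAP Table 4-2, rows 2 and 4 | not applicable | event at death |

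The protocol sentence stands alone against the other three sources. DOR is not affected, because a responder has an evaluation by definition. ORR is not a time-to-event endpoint.

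Table 4-2 has loose ends of its own. Row 1 (no baseline assessment) censors at Day 1 with no exception for death. A patient who is never scanned and dies after two or more missed assessments escapes row 2 but does not meet row 4.

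**2. Size if the protocol sentence were followed (illustration only)**

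Inputs:
- first scheduled scan at week 9 (protocol 10.3.1): 63 / 30.4375 = 2.07 months
- 20 patients per arm (protocol 6.1)
- 3-month OS 0.93, 95% CI 0.84 to 1, from the investigator-sponsored trial (protocol synopsis)
- median OS 14.0 months, lower limit 10.8, and median PFS 4.2 months, from the lenvatinib plus pembrolizumab study (protocol 4.2)

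Assumptions: exponential survival, and no scan before week 9.

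Risk of death before week 9:
- from 3-month OS: 1 − 0.93^(2.07/3) = 4.9%; at the CI limits, 1 − 0.84^(2.07/3) = 11.3%, and 0% at 1
- from median OS: 1 − 2^(−2.07/14.0) = 9.7%; at the lower limit, 1 − 2^(−2.07/10.8) = 12.4%

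The cited figures therefore span about 0% to 12%. The two point estimates give 20 × 0.049 = 1.0 and 20 × 0.097 = 1.9 expected deaths per arm.

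Effect on the median: with k of 20 patients censored at time zero, the reported curve after the first scan is S(t) / (1 − k/20). Setting this to 0.5 gives

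reported median = m × [1 + log2(1 / (1 − k/20))].

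- k = 1: log2(1/0.95) = 0.0740. OS 14.0 × 1.0740 = 15.0 months; PFS 4.2 × 1.0740 = 4.5 months.
- k = 2: log2(1/0.90) = 0.1520. OS 14.0 × 1.1520 = 16.1 months; PFS 4.2 × 1.1520 = 4.8 months.

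On the same basis, 6-month OS of 2^(−6/14.0) = 74.3% would be reported as 78.2% (k = 1) or 82.6% (k = 2). Under the SAP rule the medians stay at 14.0 and 4.2 months.

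**The case against.** The strongest reply is that the SAP governs what is run, and the SAP is right on this. Protocol section 12 measures later deviations against the final SAP, and Tables 4-1 and 4-2 count these deaths. This stands, and it limits the point: a reader might infer that early deaths will be lost from the reported OS and PFS, and the documents do not support that. It does not excuse the missing entry in SAP 1.6.

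A second reply is that the sentence does not say post-baseline. Every eligible patient has a screening scan, so nobody would lack an efficacy evaluation. The term is undefined, and this reading cannot be excluded. It would, however, leave the rule almost empty, since measurable disease is an entry criterion. Protocol 10.3 lists only imaging and response criteria as efficacy assessments, while survival status is collected under 10.6, so a missing post-baseline scan is the more natural meaning.

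Third, a recorded death is not missing data, and the specific endpoint definitions should prevail over a general default. That is sound evidence of intent, and a good reason to correct the sentence.

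Fourth, the sizes are soft:
- End-of-treatment imaging (synopsis; 10.3.1) would give some patients a scan before week 9.
- Excluding life expectancy under 4 months and requiring ECOG of at most 1 should lower early mortality.
- The one-death case pairs the investigator-sponsored trial's early risk with the other study's median. Within that trial alone, one death in 20 would move its 30.7-month median OS to 30.7 × 1.0740 = 33.0 months.
- Even if all 20 patients died, a 95% interval around 14.0 months would be 14.0 × e^(±1.96/√20), about 9.0 to 21.7 months, wider than the shift.

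All of this stands. The shift is nevertheless systematic and always favourable, while the interval reflects chance.

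Last, the version of the supplied protocol is not visible. That it is the v3.0 named in SAP 1.6 is assumed.

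**Conclusion.** The point holds as an erroneous protocol rule in undeclared conflict with the SAP. On its natural reading, the 12.1.1 sentence censors known deaths at Day 1, against the protocol's own OS and PFS definitions and the SAP's tables, and SAP 1.6 records no change.

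It is not a demonstrated bias. If the SAP is followed, deaths before the first post-baseline assessment are counted, apart from the loose ends in Table 4-2. Nor does it reach every endpoint: a reader might take the words on time-to-event analyses to put DOR at risk too, but a responder always has an evaluation. OS and PFS are secondary, summarised by medians with confidence intervals, and no hypothesis test is stated for them. The primary endpoint, ORR, is unaffected.

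The possible size, if the sentence were applied, is about 1 to 2 months on a 14.0-month median OS and 0.3 to 0.6 months on a 4.2-month median PFS, for one or two unscanned early deaths in an arm of 20. This rests on exponential survival, no scan before week 9, and early-death risks borrowed from other studies that run from about 0% to 12%. At the low end there would be no effect.

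**What to change.** Before database lock, replace the present SAP 1.6 entry with a statement that SAP Tables 4-1 and 4-2 supersede the time-to-event sentence in protocol 12.1.1. It should say that:

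- Day 1 censoring applies only to PFS, in patients who are alive and have no post-baseline tumour assessment
- a death before the first post-baseline assessment is a PFS event at the date of death
- OS never depends on tumour assessments

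In the same revision, reconcile this wording with Table 4-2: say how a death is handled when there is no baseline assessment (row 1), and when an unscanned patient dies after two or more missed assessments (row 4).

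The cost is a few sentences in the SAP. Aligning 12.1.1 itself takes a protocol amendment, which under protocol 13.1.1 requires IRB/IEC approval, with up to 20 sites involved. It can wait for the next amendment, because the SAP entry settles the analysis rule.

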12.3. Populations for Analyses

12.3.1. Modified Intent-to-treat Population

The modified intent-to-treat (mITT) population will consist of all patients who receive at least one dose of any study treatment. This population will be used for primary analyses of efficacy.

12.3.2. Safety Population

The safety population will consist of all enrolled patients who have received at least one dose of both study treatments. Patients will be analyzed according to treatment received.

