Patients will be followed for survival after the end of treatment (EoT) visit every 3 months for 12 months, or until withdrawal of consent, death, or the end of study (i.e., when the last patient in the study has been followed up on study treatment for at least 1 year, or completed at least 6 months of survival follow-up period after their last dose of study treatment, has withdrawn consent, has died, or has been lost to follow-up), whichever occurs first. End of treatment imaging will be performed ≤ 28 days after treatment discontinuation for patients who discontinue for reasons other than PD if their previous scan was performed >3 weeks before EoT.

After discontinuation of study treatment, patients will also be followed for safety 30 days after EoT and then every 3 months for 12 months and for PFS approximately every 3 months after EoT visit until PD, death or initiation of the subsequent anti-melanoma treatment (if a patient discontinues from the treatment due to reasons other than PD).

Statistical Methods:

CCI

Analysis Populations:

The modified intent-to-treat (mITT) population will consist of all patients who receive at least one dose of any study treatment.

The safety population will include all enrolled patients who receive at least 1 dose of both study drugs.

Efficacy Analyses:

The primary efficacy endpoint of ORR (proportion of patients who achieve CR or PR) will be analyzed for each arm separately on the modified intent-to-treat (mITT) population which consists of all enrolled patients who received any study treatment. Estimated ORR with 95% confidence interval (CI) will be summarized for each arm.

Analyses of other efficacy endpoints will be specified in Section 12 of the protocol and the Statistical Analysis Plan (SAP)

Safety Analysis:

Continual monitoring of safety data will be performed by the independent Data Safety Monitoring Board (DSMB). Adverse events and concomitant medications will be coded according to medical dictionary for regulatory activities (MedDRA) and WHO Drug, respectively. Safety analyses will be performed on the Safety Population and will be presented by actual treatment arm.

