12.4.2. Safety Analyses

All safety analyses will be performed on the Safety Population, unless otherwise specified and will be presented by actual treatment arm. Details of the analyses will be described in the SAP.

The safety and tolerability of selinexor will be evaluated by means of drug-related AE reports, physical examinations, and laboratory safety evaluations. The grading of the severity of the AEs will be done according to CTCAE, v.5.0. Investigators will provide their assessment as either the AE is related or not related to study drug.

Treatment-emergent AEs, SAEs, AEs of at least Grade 3 in severity, related AEs, and AEs leading to withdrawal of treatment will be summarized by Arm and in the overall safety population.

Treatment-emergent AEs will be those that start or worsen on or after the first day of study treatment, through 30 days after last dose (or the day before initiation of a new anti-neoplastic treatment, whichever occurs first). Related AEs will be those with an Investigator determination of related to study drug.

Laboratory data will be analyzed by summary statistics over time, as well as by shift tables based on severity.

Continual monitoring of safety data will be performed by the independent Data Safety Monitoring Board (DSMB). Adverse events and concomitant medications will be coded according to medical dictionary for regulatory activities (MedDRA) and WHO Drug, respectively.

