12.4.2.1. Adverse Events

Adverse events will be coded using the MedDRA and displayed in tables and listings using MedDRA system organ class (SOC) and preferred term (PT).

In those instances where the AE only has a partial date recorded, the AE will be assessed using the available date information to determine if it is treatment emergent. For AEs in which the date is completely missing, the AE will be assumed to be treatment emergent. No formal hypothesis-testing of AE incidence rates will be performed.

Adverse events will be summarized by patient incidence rates; therefore, in any tabulation, a patient contributes only once to the count for a given AE (by PT). The number and percentage of patients with any TEAE will be summarized for each cohort, classified by SOC and PT. The number and percentage of patients with TEAEs assessed by the Investigator as related to treatment will also be tabulated. The number and percentage of patients with any Grade ≥ 3 TEAE will be tabulated in the same manner.

In the event a patient experience repeat episodes of the same AE, then the event with the highest severity and/or strongest causal relationship to treatment will be used for purposes of tabulations.

SAEs will be summarized in the same manner as TEAEs.

All AEs (treatment emergent and post-treatment) will be listed in by-patient data listings, classified by cohort, patient, and day on study. In addition, separate by patient listings will be provided for the following: patient deaths; serious AEs; and AEs leading to withdrawal.

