3. PATIENT INFORMATION

3.1. Disposition of Patients and Analysis Populations

Patient disposition will be summarized in each of the following categories:

- Patients who received at least one dose of study treatment (partial or complete)
- End of treatment:
 - o Patients who were still on treatment
 - Patients who discontinued treatment and primary reason for treatment discontinuation
- Survival follow-up status
 - o Patients who discontinued treatment and entered survival follow-up
- End of study:
 - o Patients who discontinued treatment and were still on study
 - Patients who discontinued from the study and the primary reasons for study discontinuation

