3.1.1. Modified Intent-to-Treat Population

The modified intent-to-treat (mITT) population will consist of all patients who receive at least one dose of any study treatment. This population will be used for primary analyses of efficacy.

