3.4. Extent of Study Treatment Exposure and Compliance

The extent of study treatment exposure and compliance will be summarized in the safety population.

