5. SAFETY

All safety analyses will be reported by the actual treatment arm patients received and overall, among patients in the safety population.

Safety analyses will be based on the reported AEs and other safety information, such as clinical laboratory assessments including hematology and serum chemistry, vital signs, and physical examination.

The observation period will be divided into the following periods:

- The pre-treatment period is defined as the time from the signed informed consent date up to first dose of study treatment.
- The treatment period is defined as the time from first dose of study treatment to last dose of study treatment + 30 days inclusive, or start of new anti-neoplastic therapy exclusive, whichever occurs first.
- The post-treatment period is defined as the time beyond the treatment period.

All safety analyses will be performed using the following common rules:

- Safety data in patients who do not belong to the safety population (e.g., enrolled but did not receive any dose of study treatment, partial or complete) will be listed separately.
- The baseline value is the last available value before the first dose of study treatment.
- The analyses of the safety variables will be descriptive, and no systematic statistical testing is planned.

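### The safety population requires a dose of both drugs, so a patient who received only one counts for efficacy but is missing from every safety-set summary table

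*Protocol*

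**What the plan says.** The safety population is defined in three places, each requiring both drugs:

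- Protocol 12.3.2: "The safety population will consist of all enrolled patients who have received at least one dose of both study treatments". SAP 3.1.3 repeats this wording.
- Protocol 3.1 (Synopsis): "The safety population will include all enrolled patients who receive at least 1 dose of both study drugs".

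The efficacy population has a wider entry rule. SAP 3.1.1, matching Protocol 12.3.1, reads: "The modified intent-to-treat (mITT) population will consist of all patients who receive at least one dose of any study treatment".

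The safety tables are then tied to the narrower set. Protocol 12.4.2 states: "All safety analyses will be performed on the Safety Population, unless otherwise specified". The opening of SAP 5 applies the same restriction to the whole section, which covers adverse events, deaths, laboratory data and vital signs. SAP 3.4 adds: "The extent of study treatment exposure and compliance will be summarized in the safety population".

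SAP 5 also says that safety data from patients outside the safety population are to be listed separately. Its only example of such a patient is one who was "enrolled but did not receive any dose of study treatment, partial or complete".

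**The concern.** Safety and tolerability of the combination is a stated secondary objective. A patient dosed with one drug has been exposed to study treatment and can have a treatment-emergent event, yet contributes to no incidence table.

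The reason for missing the second drug matters. If it was withheld because of a reaction to the first, or because the patient died or withdrew, entry to the safety population depends on something that happened after dosing. The rule then tends to remove patients with the earliest toxicity, and reported rates fall. If the one-drug patient had no event, the rate rises slightly instead. In both cases the safety tables omit a treated patient whom the efficacy tables include.

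The tables may also disagree. A death in such a patient is an event for OS, which is analysed on mITT (SAP 4.3.2), but is absent from the death overview in SAP 5.2.

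**Working it through.** The plan states no figure to reproduce here. The check has two parts: where a one-drug patient falls under the text, and how much one exclusion moves a rate.

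**1. Where a one-drug patient appears**

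| Output | Population or rule | Included? |
|---|---|---|
| Disposition | Any dose (SAP 3.1) | Yes |
| ORR, CRR, DCR, PFS, OS | mITT (SAP 4.2.1, 4.3.2) | Yes |
| AE, laboratory and death summaries | Safety population (Protocol 12.4.2, SAP 5) | No |
| Exposure and compliance | Safety population (SAP 3.4) | No |
| By-patient AE listings | Protocol 12.4.2.1: "All AEs (treatment emergent and post-treatment) will be listed in by-patient data listings" | Yes |
| Safety data outside the safety population | Separate listing (SAP 5) | Yes, listing only |

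Protocol 12.4.2 leaves room for exceptions, but neither document gives one for these summaries.

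Other parts of the SAP fit an either-drug rule better. SAP 2.3 counts either selinexor or pembrolizumab as study treatment and takes the earliest non-zero dose as the start. The treatment and TEAE periods (SAP 5, 5.1.1.1) run from that date. The disposition category in SAP 3.1 is: "Patients who received at least one dose of study treatment (partial or complete)". The no-dose example in SAP 5 also fits an either-drug rule better, although one example does not prove intent.

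**2. Effect of excluding one patient**

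Inputs: 20 patients per arm and about 40 overall (Protocol 6.1). One excluded patient is an assumption. Let k be the number of patients with the event among all those treated.

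- Arm, excluded patient had the event: k/20 − (k−1)/19 = (20−k)/380 (fall).
- Arm, excluded patient had no event: k/19 − k/20 = k/380 (rise).
- Overall, excluded patient had the event: k/40 − (k−1)/39 = (40−k)/1560 (fall).

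| k in arm of 20 | Fall if the excluded patient had the event | Rise if not |
|---|---|---|
| 1 | 19/380 = 5.0 points (1/20 = 5.0% becomes 0/19 = 0%) | 1/380 = 0.3 |
| 5 | 15/380 = 3.9 | 5/380 = 1.3 |
| 9 | 11/380 = 2.9 (45.0% becomes 8/19 = 42.1%) | 9/380 = 2.4 |
| 10 | 10/380 = 2.6 (50.0% becomes 9/19 = 47.4%) | 10/380 = 2.6 |

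The rows k=9 and k=10 bracket the 47% rate of Grade 3 or higher TEAEs that Protocol 4.4 cites for 80 mg once weekly. That rate comes from a selinexor study in glioblastoma, so it is only a guide.

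Overall (n=40), the fall is 39/1560 = 2.5 points at k=1, 22/1560 = 1.4 at k=18 and 20/1560 = 1.3 at k=20.

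Exact (Clopper-Pearson) 95% intervals for scale: 1/20, 0.1% to 24.9%; 0/19, 0% to 17.6%; 9/20, 23.1% to 68.5%; 8/19, 20.3% to 66.5%.

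**3. Chance that the rule is ever triggered**

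The documents give no basis for the chance p that a patient receives only one drug. Over an assumed range, the probability of at least one such patient among 40 is 1 − (1−p)^40: 33% at p=1%, 64% at 2.5%, 87% at 5% and 98.5% at 10%. The expected numbers are 0.4, 1, 2 and 4.

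**The case against.** The strongest reply is that the requirement for both drugs may be deliberate. It is stated consistently in three places, and the objective concerns the combination regimen, so a combination-exposed set is a coherent choice. Both drugs are scheduled for Day 1, so a patient would have to stop between two first doses planned for the same day; there may be none. The data would not be hidden, because SAP 5 requires a separate listing and Protocol 12.4.2.1 lists all adverse events by patient. Response, PFS and OS use mITT and are unaffected. SAE reporting and DSMB review do not depend on the analysis set, so patient protection is not at issue. Given the SAP 5 example, a programmer might even build an either-drug set in practice.

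Most of this stands as a limit on size. It does not remove the problem. A listing makes the patient visible but does not put the patient into an incidence table or its denominator. A combination-exposed set can be kept as a supportive table, but as the main safety set it lets a post-dose outcome decide membership. If the wording could be programmed in two ways, that is a further reason to settle it.

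**Conclusion.** The concern holds. Followed as written, the plan drops a one-drug patient from the adverse event, laboratory, death, exposure and compliance summaries while keeping that patient in the efficacy analyses, and the reason for the exclusion can be early toxicity, death or withdrawal.

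The likely effect is small. With one excluded patient per arm of 20 (an assumption), the rate falls by at most 5.0 points in the arm; with one excluded patient among 40, it falls by at most 2.5 points overall. For events as common as the cited Grade 3 or higher rate, the falls are under 3 points in the arm and about 1.4 overall. All are well inside the sampling uncertainty. The effect matters most for a rare serious event, where losing one patient can take the event out of the table altogether. The primary ORR analysis is not affected. The point should be corrected, but it does not threaten the trial's main conclusion.

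**What to change.** In the synopsis, Protocol 12.3.2 and SAP 3.1.3, define the safety population as all patients given at least one dose of either selinexor or pembrolizumab. In effect this changes one word in each place. The no-dose example in SAP 5 then agrees with the definition. If a combination-exposed view is wanted, add a supportive table restricted to patients who received both drugs.

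No new data or assessments are needed. Two of the three edits are to the protocol, and Protocol 13.1.1 requires IRB/IEC approval of amendments. The lighter route is the one Protocol 12 allows: describe the change in the SAP. SAP 1.6, which now reports no modifications to the protocol's statistical section, would then need an entry, and the protocol text could be aligned at the next amendment. The change should be made before database lock, so that the choice of population is not made once the affected patients are known.
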